6.2 Visits and Assessments

All visits must be monitored for safety and AEs recorded.

6.2.1. Screening visit

Screening visits can be scheduled over the course of 4 weeks prior to the baseline visit.

Study activities performed:

Informed consent, [REDACTED], concomitant medication assessment, demography (age, sex, profession, level of education), medical/surgical history, inclusion/exclusion criteria check, MINI, pregnancy test, physical examination (including weight, height, calculated BMI, vital signs [body temperature, heart rate, supine BP, RR]), clinical laboratory tests, 12-lead ECG, AISRS and CGI-S, CAARS-O-RS, C-SSRS (Screening), and record adverse events. If eligible for participation, the subject is also given a diary at least 7 days prior to the scheduled baseline visit and instructed on its use. Subjects will be shown the cognitive performance tests and receive training in how to complete them at the Screening visit.

6.2.2. Baseline (within 3 days of Day 1, [\pm 1 day])

The baseline visit (also called Day -1) should be the nearest day to the first day of dosing (i.e., Day 1). Because clinics may be closed on the weekends, a Friday visit is allowed for subjects whose Day 1 is on Monday.

Study activities performed:

[REDACTED] vital signs, cognitive performance tests, AISRS and CGI- S, ASRS and CAARS-L-SR, C-SSRS -SLV, record adverse events and concomitant medications, check daily diary.

After completion of the study activities above, the inclusion/exclusion criteria are verified.

6.2.3. Day 1 dosing (\pm 1 day)

Randomization to MM-120 or placebo will occur before the first dose on Day 1. The first dose must be administered in the clinic. For this visit, the subject will remain at the testing facility for 6 hours after drug administration for blood sampling and getting familiar with the effects of LSD.

Study activities performed before dosing:

[REDACTED] vital signs, pregnancy test, C-SSRS (Since Last Visit), record adverse events and concomitant medications, check daily diary.

Study activities performed after dosing:

Blood samples for PK are taken repeatedly at 0, 0.5, 1, 2, 3, 4, 6 hours after dosing. Pharmacodynamics are measured over 6 hours including subjective effects as assessed using VAS scales, blood pressure and heart rate. 12-lead ECG will be performed at 2 hours post dosing. The 5D-ASC and MEQ30 are assessed 6 hours after dosing.

6.2.4. Post Day 1 dosing visits

Following Day 1 dosing, all visits may be conducted remotely per Investigator decision as long as all activities can be conducted per protocol, e.g., calibrated blood pressure cuff, cognitive scale.

Any visit conducted remotely due to COVID-19 requires Sponsor Medical Monitor and operations team notification and conduct under urgent safety measures and all protocol deviations captured in EDC designated COVID-19 deviation.

The reason for a remote visit must be captured in the EDC. The site will choose one of the following reasons:

1. COVID-19
2. Convenience for study subject
3. Site space considerations to conduct in clinic visits
4. Other

6.2.4.1 Week 2 visit

At the first visit after 1 week of treatment (Day 8 or after), AISRS and CGI-S will be conducted in addition to other required study activities. These activities will be performed pre-dose on the 3rd dosing visit.

6.2.4.2 Twice weekly dosing

Dosing (placebo/MM-120) must be completed by a trained study personnel with delegated authority for drug dispensing/ dosing. At each visit, adverse events and concomitant medications will be recorded, vital signs, C-SSRS (Since Last Visit) administered, and daily diary checked. Pregnancy testing will occur predose at each dosing visit or a minimum of once weekly.

6.2.4.3 Every 2 weeks prior to first dose of the week

At each visit that occurs every 2 weeks, clinical laboratory tests, ASRS and CAARS-L-SR, and pregnancy test will be conducted. [REDACTED]

[REDACTED] When combined with a dosing visit, regular activities scheduled to be conducted at each dosing visit will also be completed (see Section 6.2.4.2).

6.2.4.4 Week 6 (last dose)

Study activities performed before dosing:

[REDACTED] C-SSRS (Since Last Visit), record adverse events and concomitant medications, check daily diary, physical examination (including weight, height, calculated

BMI, vital signs [body temperature, heart rate, supine BP, RR]), cognitive performance tests, clinical laboratory tests, ASRS and CAARS-L-SR, AISRS, and CGI-S.

Study activities performed after dosing:

12-lead ECG conducted at 2 hours post dosing. Pharmacodynamics using 5D-ASC and MEQ30 at 6 hours after dosing (subject completes at home).

6.2.5. Week 10 follow-up / End of Study or Early Termination (if subject withdraws before last follow-up visit [\pm 3 days])

The Week 10 follow-up visit may be conducted remotely per Investigator decision. The reason for conducting the visit remotely must be recorded in the EDC (as listed in Section 6.2.4), and if the reason is due to COVID-19, the Sponsor Medical Monitor and operations team must be notified and the visit conducted under urgent safety measures and all protocol deviations captured in the EDC.

Pregnancy test, end of study physical examination (including weight, height, calculated BMI, vital signs [body temperature, heart rate, supine BP]), clinical laboratory tests, ASRS, CAARS-L-SR, AISRS, CGI-S, C-SSRS (Since Last Visit) will be conducted at the last visit, adverse events and concomitant medications will be recorded, and daily diary checked.

6.2.6. ADHD assessments

6.2.6.1 Adult ADHD Investigator Symptom Rating Scale

The Adult ADHD Investigator Symptom Rating Scale (AISRS) is a clinician-administered scale that assesses each of the DSM-5 symptoms of ADHD. The AISRS not only uses the adult ADHD prompts from the Adult ADHD Clinical Diagnostic Scale (ACDS) v1.2, but each of the stem questions are designed to better capture symptoms of the disorder as they present in adulthood. It has been used and validated many times in a variety of clinical drug trials.

The AISRS total score consists of 18 items from the original ADHD-RS, which were derived based on DSM- 5 criteria for ADHD. The ADHD-RS includes 9 items that address symptoms of inattention, and 9 items that address symptoms of impulsivity and hyperactivity. Each item is rated from 0 to 3. The AISRS total score can range from 0 to 54. A higher score corresponds to a worse severity of ADHD.

6.2.6.2 Clinical Global Impression – Severity scale (Investigator Assessed)

The Clinical Global Impression (CGI) rating scales are measures of symptom severity, treatment response, and the efficacy of treatments in treatment studies of subjects with ADHD. The scale has been validated.

The Clinical Global Impression – Severity scale (CGI-S) is a 7-point scale that requires the clinician to rate the **severity of the subject's illness** at the time of assessment. Possible ratings are:

- normal, not at all ill

- borderline mentally ill
- mildly ill
- moderately ill
- markedly ill
- severely ill
- among the most extremely ill subjects

The CGI-S is administered by a trained investigator.

6.2.6.3 Adult Attention-Deficit/Hyperactivity Disorder Self-Reporting Rating Scale

The Adult Attention-Deficit/Hyperactivity Disorder Self-Reporting Rating Scale (ASRS) was developed in conjunction with the World Health Organization (WHO), and the Workgroup on Adult ADHD. The ASRS has 18 questions, which are consistent with the DSM-5 criteria, and address ADHD symptoms in adults. The ASRS was externally validated on approximately 60 adult subjects and showed high internal consistency and high concurrent validity with the physician administered ADHD rating system. Self-rating scales are generally useful tools because they create a way to collect a large, accurate amount of data in an organized, quick, and cost-effective way.

It uses a scale that ranges from 0-4 based on the individuals mark in either "never, rarely, sometimes, often, very often" column for a possible total score of 72. Each column is used to describe the severity of the individual's symptoms based on the question asked. The participant is asked to make a mark within one column for each question that best describes their answer. The questions are split up into 2 separate parts; Part A consists of questions 1-6, and Part B consists of questions 7-18. If four or more answers are scored "positive" then a high consistency of ADHD is indicated and further follow-up with a licensed clinician is necessary. Positive scores in Part B can be further identifying cues of the individual's symptoms.

There have been studies done to test the validity and reliability of the ASRS by comparing results of participants that were diagnosed with childhood ADHD, after completing the self-reporting on their own, and then were subsequently tested with a clinician. There was a high correlation between the grouped symptoms (hyperactivity/impulsiveness and inattentiveness) when comparing the administration results of the tests. After an experiment with 60 adults whom completed the self-rating scale, and whose results were compared to their ratings with an administered ADHD rating scale, the results showed that the self-rating scale has a high internal reliability and also validity.

6.2.6.4 Connors' Adult ADHD Rating Scale

The Connors' Adult ADHD Rating Scale (CAARS) Self-Report Long Form (CAARS-L-SR) is a 66-item measure of ADHD symptoms that was designed as a self-report assessment for adult ADHD. Responses are scored on a 4-point scale, where 0 = not at all, 1 = just a little, 2 = pretty much, and 3 = very much. Test – retest reliabilities have been shown to be strong. The CAARS is highly correlated with other self-report ADHD measures, and initial studies on diagnostic accuracy for adult ADHD found the CAARS to have a good diagnostic sensitivity

and specificity relative to healthy controls. The Connors' Adult ADHD Rating Scale Observer Short Screening (CAARS-S-OR) version will be used during screening. The 30-item version includes DSM-IV criteria for ADHD and takes approximately 10 min to complete. The scale yields scores for 1) inattentiveness, and 2) hyperactivity/impulsivity symptoms according to DSM-IV, and 3) an ADHD index which allows best to differentiate between persons with ADHD and normal persons. Item scores are summed to three main scores which are then transformed using population-derived age- and sex-adjusted norm values to a T-score. A T-score < 60 indicates no ADHD. A T-score of 60-64 indicates borderline ADHD. A T-score of > 64 indicates ADHD.

6.2.7. Daily Diary

To explore sleep quality and duration, the subjects will be given a home diary for recording sleep parameters. Details of the home diary will be described in a separate document. Analysis will be specified in the SAP.

6.2.8. Cognitive Performance Tests (Computer Test)

The cognitive performance tests are objective measurements of attention to a task(s). Tests are performed at Baseline and Week 6 (prior to last dose).

6.2.8.1 Stop-signal task

The stop-signal task requires subjects to make quick key responses to visually presented go signals, and to inhibit any response when a visual stop signal is presented (Fillmore et al., 2002; Kuypers et al., 2007). The go signals are four 1.5 cm letters (A, B, C, D) presented one at a time in the center of a computer screen.

A single test consists of 176 trials in which each of the four-letter stimuli will be presented equally. A stop signal occurs in 48 trials during a test. The stop signal consists of a visual cue, i.e., “*”, that appears in one of the four corners of the screen. The subjects are required to withhold any response in case a stop signal is presented. The task has a duration of 10 minutes. The dependent variables are the proportion of correct Go and Stop responses, and the stop reaction time. The stop reaction time (SSRT) to stop signal trials represent the estimated mean time required to inhibit a response. The SSRT is used as a clinical index of inhibitory control, primarily in the study of ADHD, where impulsive subjects have slower SSRTs (Logan et al., 1997; Oosterlaan et al., 1998; Rubia et al., 1998). Higher numbers indicate more difficulty inhibiting responses. Task duration is 10 minutes.

6.2.8.2 Discounting task

In the delay discounting task subjects are presented 114 questions. For each question, subjects have to indicate which of two hypothetical rewards they prefer, the ‘standard’ or the ‘alternative’ item. The standard item, 100 Swiss francs, is available after one of five delays (0, 7, 30, 180, or 365 days). The alternative item is an amount of money (1, 25, 50, 100, 150, 200, 250, 300, 350, 400, 450, 500, 550, 600, 650, 700, 750, 800, 850, 900, 950, 1000, or 1050 Euros (Maastricht site)/Swiss francs (Basel site) available after 0 days). Each combination of standard and alternative item is only used once and presented in random order. Subjects are asked to

express their preference for an item by pressing one of two buttons. Recorded response choices are used afterwards to calculate the switch points per delay at which the subject preferred the alternative item over the standard item. Task duration is 10 minutes. Previous research demonstrates excessive delays discounting among individuals with ADHD (Kuypers et al., 2007; Mitchell, 1999).

6.2.8.3 Psychomotor vigilance task

The psychomotor vigilance task (PVT) is a sustained attention task, measuring reaction time in response to a visual stimulus over a period of 10 minutes. Subjects have to react to the onset of a counter as quickly as possible by pressing a response button. Outcome measures are mean reaction time (milliseconds) and number of attention lapses, defined as a failure to react, or any reaction exceeding 500 msec (Dinges et al., 1985).

6.2.8.4 Time Production task

During the time production (TP) task (Hurks et al., 2014), an aspect of time perception is measured, namely the ability to estimate and produce the duration of a time interval that is presented in numbers. Subjects are presented with a stimulus depicting a candle and a number indicative of a time interval (3, 6, 12, 15, 30, or 45 seconds). When this stimulus appears, subjects have to press the space bar and are asked to hold the button as long as the number next to the candle indicates (e.g., 12 s). As soon as the space bar is released, the stimulus disappears from the screen and the procedure repeats itself. The six-time intervals (3, 6, 12, 15, 30, or 45 seconds) will be presented twice in random order, summing up to 12 trials in total. It will take about 5 minutes to complete the task. Dependent variables include the mean duration judgement ratio score; first the duration judgement ratio is calculated by taking the ratio of subjective and objective duration in milliseconds (i.e., the duration judgment ratio) for each trial; these are averaged for each stimulus duration (i.e., 3, 6, 12, 15, 30, or 45 seconds). A score smaller than 1 represents an underestimation of the stimulus duration, whereas a score larger than 1 represents an overestimation of the stimulus duration. A mean score will be calculated by averaging all six duration judgment scores.

6.2.8.5 Time Reproduction task

During the time reproduction (TR) task (Hurks et al., 2011), the ability to reproduce a time interval is measured. During this task, subjects will be shown a stimulus (i.e., a row of light bulbs, of which only one is turned on) that is presented for a certain time interval (3, 6, 12, 15, 30, or 45 seconds). This stimulus is followed by a fixation point for 1000 milliseconds. After this, the same stimulus (i.e., a row of light bulbs, of which only one is turned on) is shown again. Once the row of light bulbs appears, subjects have to press the space bar and hold this for as long as the row of light bulbs appeared to them before, thereby reproducing the time interval. As soon as the space bar is released, the light bulb switches off and the procedure repeats itself. The Good Distribution Practice six-time intervals (3, 6, 12, 15, 30, or 45 seconds) will be presented twice in random order, summing up to 12 trials in total. It will take 10 minutes to complete the task. Dependent variables include the mean duration judgement ratio score; first the duration judgement ratio is calculated by taking the ratio of subjective and objective duration in milliseconds (i.e., the duration judgment ratio) for each trial; these are averaged for each stimulus duration (i.e., 3, 6, 12, 15, 30, or 45 seconds). A score smaller than 1 represents

an underestimation of the stimulus duration, whereas a score larger than 1 represents an overestimation of the stimulus duration. A mean score will be calculated by averaging all six duration judgment scores.

7. SAFETY

7.1 Physical Risks to the Subjects

MM-120 use is not associated with any known physical risks, but it may produce psychiatric complications as described above and below.

7.1.1. Expected acute adverse effects

The low dose (20 µg) of MM-120 used in the present study is expected to produce minimal subjective and physiological acute adverse effects, including subtle acute feelings of drug effect, and slight impairment of cognition (Bershad et al., 2019; Yanakieva et al., 2019). Very susceptible persons could potentially experience effects more typically experienced with high doses of LSD, including dysphoria, anxiety, mood swings, dream-like state, transient depersonalization and derealization phenomena, mild and transient paranoid thinking, negative experiences (anxiety, dysphoria, bad trips), tremor, restlessness, acute perceptual changes, acutely impaired psychomotor function, mild tachycardia, mild hypertension, nausea, headache, dizziness, trembling, lack of appetite (Dolder et al., 2016; Gasser, 2012b; Johnson et al., 2012; Passie et al., 2008; Schmid et al., 2015; Studerus et al., 2011). Adverse effects at a dose of 100 µg are expected to completely subside within 24 h at most (Dolder et al., 2016). No severe or serious adverse effects are expected based on previous studies using a 20 µg dose of MM-120.

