7.6.3. Unexpected Adverse Reaction

An Unexpected Adverse Reaction (UAR) is an adverse reaction (AR), the nature or severity of which is not consistent with the applicable product information (e.g., Investigator's brochure [IB] for an unapproved investigational product or summary of product characteristics [SmPC] for an authorized product). When the outcome of the adverse reaction is not consistent with the applicable product information, this adverse reaction should be considered as unexpected. Side effects documented in the IB, or SmPC which occur in a more severe form than anticipated, are also considered as being unexpected.

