7.6.5. Suspected Unexpected Serious Adverse Reaction

A Suspected Unexpected Serious Adverse Reaction (SUSAR) is any suspected adverse reaction related to an IMP that is both unexpected and serious.

The Investigator evaluates SAEs for seriousness and causality in consultation with the Sponsor Medical Monitor, as necessary. Expectedness is also determined by the Sponsor's Medical Monitor based on an assessment of the adverse event in the context of previously reported adverse events, as outlined in the Investigators' Brochure and/or study protocol. If the event is related to the IMP and is both serious and unexpected, it is classified as a SUSAR.

For purposes of defining a SUSAR, any SAE that has a causality of "possibly", "probably" or "definitely" will be considered to be related to the IMP.

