7.7 Causality

Most adverse events and adverse reactions that occur in this study, whether they are serious or not, will be expected treatment-related toxicities due to the medication used in this study. The assignment of the causality will be made by the Investigator using the definitions in the table below.

Relationship	Description
Unrelated	There is no evidence of any causal relationship.
Unlikely	There is little evidence to suggest there is a causal relationship (e.g., the event did not occur within a reasonable time after administration of the IMP). There is another reasonable explanation for the event (e.g., the participant's clinical condition, other concomitant treatment).
Possible	There is some evidence to suggest a causal relationship (e.g., because the event occurs within a reasonable time after administration of the IMP). However, the influence of other factors may have contributed to the event (e.g. the participant's clinical condition, other concomitant treatments).
Probable	There is evidence to suggest a causal relationship and the influence of other factors is unlikely.
Definitely	There is clear evidence to suggest a causal relationship and other possible contributing factors can be ruled out.

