7.8.2. SAE and SUSAR reporting

Should a SAE occur, the Principal Investigator (PI) will be informed and relationship to the study drug will be assessed by the PI using the definitions shown above. Complete information concerning the SAE will be collected by the PI and documented on a standard SAE form. SAE leading to death will be reported to the EC by the PI within 7 days. SUSARs leading to death or any other SUSARs will be reported to the EC within 7 and 15 days respectively.

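### Section 7.7 presumes that most events, serious ones included, are expected and drug-caused, which contradicts 7.1.1 and could support not classing a related serious event as a SUSAR

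*Protocol*

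**What the plan says.** Protocol 7.1.1 lists the acute effects to be anticipated and closes by saying of the 20 µg dose: "No severe or serious adverse effects are expected based on previous studies". Section 7.1, directly above it, says "MM-120 use is not associated with any known physical risks", and adds that psychiatric complications may occur.

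Section 7.7 begins: "Most adverse events and adverse reactions that occur in this study, whether they are serious or not, will be expected treatment-related toxicities". Its next sentence tells the investigator to assign causality from the definitions in the table that follows.

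Two sections say what expectedness is judged against:

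- Section 7.6.3 calls a reaction unexpected when it is one "the nature or severity of which is not consistent with the applicable product information", with the Investigator's Brochure as the example for an unapproved product. A documented effect that turns out more severe than anticipated also counts as unexpected.
- Section 7.6.5 has the Sponsor's Medical Monitor assess the event "in the context of previously reported adverse events, as outlined in the Investigators' Brochure and/or study protocol". A related event that is both serious and unexpected is a SUSAR.

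On timing, 7.8.2 says: "SUSARs leading to death or any other SUSARs will be reported to the EC within 7 and 15 days respectively". It also requires fatal serious adverse events to go to the ethics committee within 7 days. It sets no ethics-committee deadline for other serious events.

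**The concern.** The two statements cannot both guide a judgement about a serious event. Section 7.1.1 says none is expected; 7.7 expressly includes serious events among those it calls expected. Because 7.6.5 admits the protocol as a reference, both statements sit inside a permitted source. At stake is whether a related, non-fatal serious event is treated as a SUSAR.

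The 7.7 sentence also tells blinded investigators, just before they rate causality, that most of what they will see is caused by the drug. In a 1:1 placebo-controlled trial that prejudges the rating. Causality ratings determine which events enter the by-arm tables of related events and serious adverse reactions (protocol 7.6.4; SAP 8.11.1.4, 8.11.1.8 and 12.8.1).

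**Working it through.** The plan gives no figure to reproduce. The main check applies the protocol's own SUSAR rule to one event under each statement.

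**Rule (7.6.5).** SUSAR = related and serious and unexpected. Related means possible, probable or definite.

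**Test case.** Take a related, non-fatal serious event. The first two conditions are met, so only expectedness is open.

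| Reference applied | Expected? | Class | Ethics-committee deadline in 7.8.2 |
|---|---|---|---|
| Protocol 7.1.1 | No: nothing serious is expected at 20 µg | SUSAR | 15 days |
| Protocol 7.7 | Can be argued yes | Serious adverse reaction, not a SUSAR | None stated |
| Investigator's Brochure only | Depends on the brochure, which is not among the documents | Cannot be determined here | Cannot be determined here |

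**Fatal event.** It is due within 7 days as a fatal serious adverse event and within 7 days as a fatal SUSAR. The conflict does not change this deadline.

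**Other consequences.** The class can bear on whether the sponsor unblinds the case for expedited reporting (protocol 5.1) and whether it appears in the listing of unexpected reactions and SUSARs (SAP 12.8.1). SAP 8.11.1.5 and 8.11.1.6 do not resolve the conflict: they repeat the product-information test and leave expectedness to the sponsor.

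**Causality presumption.** Allocation is 26 and 26 (protocol 3.1). Let *p* and *a* be the mean numbers of events per subject on placebo and on MM-120. Assume that background events are equally frequent in both arms, so that *a* − *p* is due to the drug. The drug-caused share of all events is

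26(*a* − *p*) / [26(*a* + *p*)] = (*a* − *p*)/(*a* + *p*).

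This exceeds one half only if *a* > 3*p*. For *most* events to be drug toxicities, the MM-120 arm would need more than three times the placebo event rate. The documents do not predict that. Section 7.1.1 anticipates minimal acute effects. Section 1.5 cites a repeated-dose study of 5–20 µg in older healthy adults in which events were no more frequent than on placebo; with *a* = *p* the share is 0. It is not impossible either, because 7.6.1 counts even pleasant drug effects as adverse events. The sentence is therefore an unsupported prediction rather than a demonstrable falsehood. For the placebo arm it cannot hold at all.

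**7.1 against 7.1.1.** Section 7.1 denies known physical risks. Section 7.1.1 names tremor, mild tachycardia, mild hypertension, nausea and headache as possible in very susceptible persons, and 7.4.2 says transient headaches may occur.

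**The case against.** The strongest reply is that 7.7 outlines no events. Section 7.6.5 asks for an assessment against previously reported events as described in the reference, and a sentence about most events that names none cannot show that a particular event is expected. Section 7.6.3 ties the test to product information and treats greater-than-anticipated severity as unexpected. The decision belongs to the Medical Monitor, not to the site staff who read 7.7. This stands, and it limits the consequence. A reader might infer that 7.7 fixes the reporting class of every related non-fatal serious event; the documents do not support that. They show only that the sentence is available as an argument.

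On causality, the reply is that investigators are told to use the table, whose definitions rest on evidence, timing and alternative explanations. No inference on safety is planned (protocol 13.6.7), and the overall event tables do not depend on relatedness. This also stands. A reader might infer that the sentence inflates the related-event tables or blurs the contrast between arms. That is plausible, but nothing in the documents shows it or lets it be sized.

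A third reply is that the sentence speaks of events in the study as a whole and could hold if most events occur on active drug. The threshold above shows how large the imbalance would have to be. Even if it came about, that would be a result of the trial, not a premise for rating causality.

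None of these replies reconciles 7.7 with 7.1.1 or explains why 7.6.3 and 7.6.5 name different references.

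**Conclusion.** The point holds as a wording contradiction in operative safety text. Section 7.7 conflicts with 7.1.1 on whether serious events are expected, and 7.6.5 permits the protocol to be used as the reference. The conflict could therefore take a related, non-fatal serious event out of the 15-day SUSAR report. It need not do so, and it changes no deadline for a fatal event. The route depends on the Medical Monitor using the protocol as a reference; if only the Investigator's Brochure is used, the conflict does not reach the classification.

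The prejudgement of causality stands independently of which reference is used. Its effect is of unknown size and confined to outputs that depend on relatedness, which are descriptive. No efficacy analysis is affected.

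A reader might also conclude that the brochure should become the sole reference. The documents do not support that step. The brochure cannot be inspected here, and if it lists a serious reaction as expected, the change could reduce SUSAR reports.

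**What to change.** 1. Delete the first sentence of 7.7. Causality then rests only on the table's definitions, and no blanket statement of expectedness remains.
2. Reconcile 7.6.3 and 7.6.5 so that both name the same reference for expectedness. Which document that is remains the sponsor's choice. Keep the 7.1.1 position that no serious effects are expected unless the reference safety information says otherwise.
3. Reconcile the opening statement of 7.1 with the physical effects listed in 7.1.1 and the headaches in 7.4.2.

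The cost is one deleted sentence and small wording changes in the other sections. No visit, dose, endpoint or analysis changes.
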